## 9.5 SAMPLED BLOOD VOLUME

No more than 7 mL/kg of blood will be collected during any 8-week period of the 64-week treatment period in all patients, regardless of age cohort. Additional blood samples may be collected at the investigator's discretion for patient safety monitoring.

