	Dose escalation visits & 2 nd infusion at highest tolerated dose				Quarterly visits (day 1/wk0, wk12, wk26, wk38, wk52)				Week 64
	Pre-infusion	End of infusion	24 hr	48 hr	Pre-infusion	End of infusion	24 hr	48 hr	
Electrocardiogram	X a	X a	X a	X a	X b	X	X c	X	
Liver function testing	X		X c	X	X		X c	X	X
Clinical chemistry & coagulation					X		X c	X	X
Urinalysis					X				X
Hematology					X d		X c	X	
Safety biomarkers:									
Ceramide	X		X c	X	X		X c	X	X
Cardiac troponin-1	X		X c	X	X		X c	X	X
hsCRP	X		X c	X	X		X c	X	X
Calcitonin	X		X c	X	X		X c	X	X
Iron and ferritin	X		X c	X	X		X c	X	X
IL6 and IL8 e	X		X c	X	X f		X c,f	X f	
Plasma and/or DBS sphingomyelin and metabolite concentrations g	X		X c	X	X		X c	X	X

Note: When multiple assessments are required, the order should be vital signs before ECG before PK or blood draws. Preinfusion assessments are to be completed within 24 hours prior to olipudase alfa infusion. End of infusion assessments are to be completed with 10 minutes following the end of olipudase alfa infusion. Twenty four (24) hour and 48 hour post infusion assessments to be completed within  $\pm$  3 hours of scheduled time.

a At each new dose of  $\geq 0.3$  mg/kg only.

b ECG in triplicate on day 1/week 0

c Sample/assessment is not required in patients in the child cohort (patients aged 6 to <12 years) or in patients aged 3 to < 6 years.

d Two samples to be collected within 24 hours of olipudase alfa at week 52. See [Section 10.3.5](#) for details.

e Sample not required in patients aged 3 to < 6 years.

f Sample not required at week 26, week 38 or week 52.

g DBS collection not required in patients aged 3 to < 6 years.

Abbreviations: hr = hour; hsCRP = high sensitivity C reactive protein; IL = interleukin; wk = week.

**1.4 SUPPLEMENTAL FLOWCHART - DAY 1/WEEK 0, DOSE ESCALATION VISITS, SECOND INFUSION AT THE HIGHEST TOLERATED DOSE, QUARTERLY VISIT AND WEEK 64 ASSESSMENTS IN PATIENTS ≤ 2 YEARS OLD**

	Day 1/Week 0			Dose escalation visits & 2 nd infusion at highest tolerated dose			Quarterly visits (wk12, wk26, wk38, wk52)			Week 64

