## **9.2 SECONDARY ENDPOINTS**

### **9.2.1 Pharmacokinetics**

#### **9.2.1.1 *Sampling time***

Pharmacokinetic sampling will occur with the first infusion at 0.3, 1.0 and 3.0 mg/kg olipudase alfa and at Week 52. Specific time points and collection time windows are detailed in [Section 1.5](#) for each age cohort. To minimize the amount of blood drawn, post-dose time points have been selected for sparse sampling of pharmacokinetic parameters and microsampling methods (volumes  $\leq$ 0.5 mL) may be used.

If a patient receives only a partial infusion (eg, due to a safety concern), pharmacokinetic sampling will be repeated the next time the patient receives that dose.

Depending on patient age, blood samples will be drawn for pharmacokinetic assessments using an indwelling catheter from an arm that is not used for olipudase alfa infusions. The exact time of olipudase alfa infusions (start and stop times of infusion), rate of infusion, time of infusion rate changes, and dose will be recorded along with exact sampling times.

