**Table 4 - Approximate sampled blood volume in ASMD patients ages 12 to <18 years (adolescent cohort).**

Assessment	Volume per sample (mL)	Screening period		64-week treatment period	
		Number of samples	Total (mL)	Number of samples	Total (mL)
SMPD1 genotyping	3	1	3		
UGT1A1 genotyping	3	1	3		
CHIT1 genotyping	3	1	3		
ASM activity in leukocytes	6	1	6		
Serology tests: HIV, Hep C, Hep B	7	1	7		
Liver function	3	1	3	43	129
Clinical chemistry	4	1	4	16	64
Hematology	4	2	8	16	64
Coagulation	5	1	5	16	80
β—hCG	2	1	2	0	
Safety biomarkers	8			43	344
Anti-olipudase alfa IgG and neutralizing antibodies in IgG positive patients	3.5			13	45.5
Efficacy biomarkers	5			4	20
Lipid profile	8	1	8	6	48
Serum bone-specific ALP and C-telopeptide	4			4	16
Sphingomyelin and metabolites in plasma and/or DBS	3			43	129
Olipudase alfa pharmacokinetics	2			28	56
Total for screening (mL)			52		
Total for 64-week treatment period (mL)					995.5
Total for study (mL)					1047.5

**Table 5 - Approximate sampled blood volume in ASMD patients in the child cohort (6 to <12 years) and in patients aged 3 to <6 years.**

Type	Volume per sample (mL)	Screening period		64-week treatment period	
		Number of samples	Total (mL)	Number of samples	Total (mL)
SMPD1 genotyping	3	1	3		
UGT1A1 genotyping	3	1	3		
CHIT1 genotyping	3	1	3		
ASM activity in leukocytes	3	1	3		
Serology tests: HIV, Hep C, Hep B	2.2	1	2.2		
Liver function	3	1	3	30	90
Clinical chemistry	4	1	4	11	44
Hematology	2	2	4	11	22
Coagulation	2.8	1	2.8	11	30.8
Safety biomarkers	6			30	180
Anti-olipudase alfa IgG and neutralizing antibodies in IgG positive patients	2.2			13	28.6
Efficacy biomarkers	3.8			4	15.2
Lipid profile	1.1	1	1.1	6	6.6
Serum bone-specific ALP and C-telopeptide	1			4	4
Sphingomyelin and metabolites in plasma and/or DBS	1.5			43	64.5
Olipudase alfa pharmacokinetics	1.5			24	36
Total for screening (mL)			29.1		
Total for 64-week treatment period (mL)					521.7
Total for study (mL)					550.8

See [Section 1.3](#) for additional information on sample collections based upon patient age.

**Table 6 - Approximate sampled blood volume in adolescent ASMD patients from birth to ≤2 years of age (infant/early child cohort).**

Type	Volume per sample (mL)	Screening period		64-week treatment period	
		Number of samples	Total (mL)	Number of samples	Total (mL)
SMPD1 genotyping	3	1	3		
UGT1A1 genotyping	3	1	3		
CHIT1 genotyping	3	1	3		

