2.7 ANALYSIS OF PHARMACOKINETIC DATA

All the pharmacokinetic analyses will be performed using the pharmacokinetic population. Pharmacokinetic sampling will occur with the first infusion at 0.3, 1.0 and 3.0 mg/kg olipudase alfa and at Week 52. Specific time points are detailed in protocol Section 1.5 for each age cohort. To minimize the amount of blood drawn, post-dose time points have been selected for sparse sampling of pharmacokinetic parameters and microsampling methods (volumes \leq 0.5 mL) will be used. If a patient receives only a partial infusion (eg, due to a safety concern), pharmacokinetic sampling will be repeated the next time the patient receives that dose.

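### Even with 0.5 mL PK samples, the 7 mL/kg per 8-week blood cap and the full Weeks 0 to 6 sampling schedule cannot both be met below about 9.9 kg (2 y or under), 15.1 to 17.0 kg (3 to <6 y), 15.3 to 17.0 kg (6 to <12 y) and 29.4 to 34.5 kg (12 to <18 y)

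*Protocol*

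**What the plan says.** Protocol Section 9.5 sets one limit for every age cohort: "No more than 7 mL/kg of blood will be collected during any 8-week period of the 64-week treatment period in all patients". Its next sentence lets the investigator take extra blood to monitor safety.

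Tables 4 to 6 list volume per sample, number of samples, and totals for screening, the treatment period and the study. Table 5 is headed "Approximate sampled blood volume in ASMD patients in the child cohort (6 to <12 years) and in patients aged 3 to <6 years". No table shows an 8-week volume or a weight below which the schedule no longer fits.

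The schedule is already thinned by age. In Section 1.3, footnote c removes the 24-hour draw: "Sample/assessment is not required in patients in the child cohort (patients aged 6 to <12 years", and it goes on to cover ages 3 to <6. Footnote e does the same for IL-6 and IL-8: "Sample not required in patients aged 3 to < 6 years". Section 10.3 rules out duplicate draws at Week 12.

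The two documents differ on PK volume. Protocol 9.2.1.1 makes microsampling optional ("0.5 mL) may be used"), SAP 2.7 makes it definite ("0.5 mL) will be used"), and Tables 4 to 6 budget 2 or 1.5 mL per PK sample.

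**The concern.** A limit on any 8-week period cannot be checked against a 64-week total. Liver tests, safety biomarkers, sphingomyelin and antibody samples are drawn at every visit of the escalation phase. Day 1 and Week 12 add the quarterly panel, and PK falls at the first 0.3, 1.0 and 3.0 mg/kg infusions.

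Enrolment is open from birth without a minimum weight, and height must be at a Z-score of -1 or lower. If a light child's scheduled blood exceeds the cap, the site must leave out tubes without a visible rule on which. Some of those tubes carry primary safety endpoints, and liver tests feed the patient stopping criteria in Section 8.3.4.2.1. Section 6.4 calls dose escalation the most critical phase for safety.

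**Working it through.** **Reproducing the plan's totals.** Treatment-period volume is the sum of volume times number of samples.
- Table 4: 129 + 64 + 64 + 80 + 344 + 45.5 + 20 + 48 + 16 + 129 + 56 = 995.5 mL.
- Table 5: 90 + 44 + 22 + 30.8 + 180 + 28.6 + 15.2 + 6.6 + 4 + 64.5 + 36 = 521.7 mL.
- Table 6: 31.9 + 8.8 + 12 + 15.4 + 132 + 14.3 + 15.2 + 6.6 + 43.5 + 30 = 309.7 mL.

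All three match the printed totals.

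**Rebuilding the schedule.** Planned doses are 0.03 mg/kg at Week 0, 0.1 at Week 2, 0.3 at Weeks 4 and 6, 0.6 at Weeks 8 and 10, 1.0 at Week 12, 2.0 at Week 14, and 3.0 from Week 16. PK falls at Weeks 4, 12, 16 and 52, with 7, 6 or 5 samples per occasion by cohort (Table 1). Draws per visit come from Sections 1.2 to 1.4 and 10.3. Day 1 pre-infusion draws count as treatment-period blood, as in Tables 4 to 6.

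The rebuild gives every Table 4 count. For example, liver tests are 10 × 3 (Weeks 0 to 18) + 3 (Weeks 20 to 24) + 3 × 3 (Weeks 26, 38, 52) + 1 (Week 64) = 43. For Tables 5 and 6 it differs only in these counts:
- Table 5 sphingomyelin: 30, against 43 printed.
- Table 6 coagulation: 8, against 11.
- Table 6 sphingomyelin: 30, against 29.
- Table 6 lipids: 4, against 6 (SAP 2.8.11 does not require Day 1 and Week 12 at 2 y or under).

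**Volume per visit, without PK.**
- 12 to <18 y, Week 0: liver 9 + chemistry 12 + hematology 12 + coagulation 15 + biomarkers 24 + antibody 3.5 + efficacy 5 + lipid 8 + bone 4 + sphingomyelin 9 = 101.5 mL. Weeks 2, 4, 6: 9 + 24 + 3.5 + 9 = 45.5 mL each.
- 3 to <12 y, Week 0, same order: 6 + 8 + 4 + 5.6 + 12 + 2.2 + 3.8 + 1.1 + 1 + 3 = 46.7 mL. Weeks 2, 4, 6: 6 + 12 + 2.2 + 3 = 23.2 mL each.
- 2 y or under, Week 0: 1.1 + 1.1 + 1.2 + 1.4 + 8.8 + 1.1 + 3.8 + 3 = 21.5 mL (no lipid or bone tube). Weeks 2, 4, 6: 2.2 + 8.8 + 1.1 + 3 = 15.1 mL each.

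**Weeks 0 to 6 with 0.5 mL PK at Week 4.** Break-even weight = volume / 7.

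| Age | Sum (mL) | Break-even |
|---|---|---|
| 2 y or under | 21.5 + 3 × 15.1 + 5 × 0.5 = 69.3 | 9.9 kg |
| 3 to <6 y | 46.7 + 3 × 23.2 + 5 × 0.5 = 118.8 | 17.0 kg |
| 6 to <12 y | 46.7 + 3 × 23.2 + 6 × 0.5 = 119.3 | 17.0 kg |
| 12 to <18 y | 101.5 + 3 × 45.5 + 7 × 0.5 = 241.5 | 34.5 kg |

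**Lower ends.**
- 3 to <6 y: no volume is given for the biomarker tube without IL-6 and IL-8. Assuming Table 6's 4.4 mL, 118.8 − 8 × 1.6 = 106.0 mL, or 15.1 kg.
- 6 y and over: Section 9.2.3 allows plasma and/or dried blood spots (DBS) for sphingomyelin. Assuming DBS alone at negligible volume, 119.3 − 8 × 1.5 = 107.3 mL (15.3 kg) and 241.5 − 12 × 3 = 205.5 mL (29.4 kg).

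**Other PK assumptions, plasma tubes kept.**
- No PK at all: 66.8, 116.3 (103.5 with the 4.4 mL tube), 116.3 and 238.0 mL, or 9.5, 16.6 (14.8), 16.6 and 34.0 kg.
- Printed PK volumes: the peak moves to Weeks 10 to 16, with 77.8, 126.5 (113.7), 129.5 and 257.0 mL, or 11.1, 18.1 (16.2), 18.5 and 36.7 kg.

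**Size at assumed weights, 0.5 mL PK.**
- 8 kg, 2 y or under: allowed 56.0 mL, scheduled 69.3 mL (24% over).
- 10 kg, 2 y or under: allowed 70.0 mL, so the schedule fits.
- 14 kg, 3 to <6 y: allowed 98.0 mL, scheduled 106.0 to 118.8 mL (8% to 21% over).

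**The case against.** **The cap has a safety allowance.** The second sentence of Section 9.5 permits additional safety samples, so one could read the cap as flexible. That sentence covers discretionary extras. It does not exempt scheduled draws, which are all that is counted here.

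**A site would drop tubes rather than breach the cap.** This stands. A reader might infer that small children will be over-bled. The documents do not support that, because the cap is a rule the site must follow.

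**A priority rule may exist.** This also stands. Most Section 1.2 footnotes are not legible in the available text. Footnote g is attached to liver, chemistry, hematology, coagulation, biomarker and sphingomyelin samples, and the study manual is not available. It would be wrong to infer that no rule exists.

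**Few patients may be affected.** Minimum enrolment under 6 years is 2 + 2, Section 4.1 places type B diagnosis typically after age 2, and E02g and E09 let an investigator exclude a child who cannot complete the evaluations. These points limit the likely exposure but set no weight floor. With no weights in the documents, neither a large nor a negligible number can be claimed.

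**The volumes are approximate, and DBS can replace plasma.** DBS makes the plasma-based limits for the two older groups upper values, hence the ranges. It does not help the younger groups: DBS is not required at 3 to <6 y, and Section 1.4 lists plasma only at 2 y or under. Rounding could matter for a 14 kg child on the smaller biomarker tube (8% over). It would not close the gap at 8 kg, where volume must fall 19% (from 69.3 to 56.0 mL). At 2 y or under, the Day 1 pre-infusion biomarker tube is counted at 4.4 mL although hsCRP is not drawn then. Any effect is under 4.4 mL, or 0.6 kg.

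**Conclusion.** The point holds as an arithmetic conflict between a stated limit and the stated schedule. With 0.5 mL PK samples, both cannot be met below about 9.9 kg at 2 y or under, 15.1 to 17.0 kg at 3 to <6 y, 15.3 to 17.0 kg at 6 to <12 y and 29.4 to 34.5 kg at 12 to <18 y. The ranges rest on the assumed 4.4 mL biomarker tube and on DBS alone at negligible volume. Microsampling does not remove the conflict, since it remains with no PK at all.

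The sums take four visits as an 8-week period and leave out screening blood, unscheduled safety samples and the 12.5 mL reaction work-up in Table 7. Including the Week 8 visit, possible within the ±3-day window, would raise the plasma-based limits to 12.1, 20.3 (18.0 with the 4.4 mL tube), 20.4 and 41.0 kg.

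The consequence is scheduled tubes left out during dose escalation, in an unknown number of children. The miscounts in Tables 5 and 6 are a separate, minor matter: a reader might take them as the cause, but they change no break-even weight.

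**What to change.** In Section 9.5:

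1. State the peak 8-week volume and the break-even weight for each age group.
2. Require PK microsampling (0.5 mL or less) under 12 years, in line with SAP 2.7.
3. For patients below the break-even weight, state an order of cuts, or cite it if it already exists. Keep liver, clinical chemistry, hematology, coagulation, antibody and safety-biomarker tubes. First drop efficacy, lipid, bone and plasma PD tubes, using DBS alone where it is collected (6 years and over). Then drop PK. Reduce safety-biomarker volume only as far as the assays allow; the documents give no assay minimums. Biomarkers are the largest component: 8 × 4.4 = 35.2 of the 69.3 mL at 2 y or under.
4. Correct the counts. Table 5 sphingomyelin 43 to 30: 521.7 − 13 × 1.5 = 502.2 mL. Table 6 coagulation 11 to 8, sphingomyelin 29 to 30 and, per SAP 2.8.11, lipid 6 to 4: 309.7 − 3 × 1.4 + 1.5 − 2 × 1.1 = 304.8 mL.

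The cuts in item 3 narrow the problem without removing it. With PK kept at 0.5 mL, the peak at 2 y or under becomes Weeks 10 to 16: 3 × 12.1 + 14.5 + 10 × 0.5 = 55.8 mL, or 8.0 kg. At 3 to <6 y it is 3 × 20.2 + 37.8 + 10 × 0.5 = 103.4 mL (90.6 with the 4.4 mL tube), or 12.9 to 14.8 kg.

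The cost is a protocol and laboratory-manual amendment, thinner PD data in the smallest patients and, at the lowest weights, thinner PK data. Both serve secondary objectives.

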**Table 4 - Approximate sampled blood volume in ASMD patients ages 12 to <18 years (adolescent cohort).**

Assessment	Volume per sample (mL)	Screening period		64-week treatment period	
		Number of samples	Total (mL)	Number of samples	Total (mL)
SMPD1 genotyping	3	1	3		
UGT1A1 genotyping	3	1	3		
CHIT1 genotyping	3	1	3		
ASM activity in leukocytes	6	1	6		
Serology tests: HIV, Hep C, Hep B	7	1	7		
Liver function	3	1	3	43	129
Clinical chemistry	4	1	4	16	64
Hematology	4	2	8	16	64
Coagulation	5	1	5	16	80
β—hCG	2	1	2	0	
Safety biomarkers	8			43	344
Anti-olipudase alfa IgG and neutralizing antibodies in IgG positive patients	3.5			13	45.5
Efficacy biomarkers	5			4	20
Lipid profile	8	1	8	6	48
Serum bone-specific ALP and C-telopeptide	4			4	16
Sphingomyelin and metabolites in plasma and/or DBS	3			43	129
Olipudase alfa pharmacokinetics	2			28	56
Total for screening (mL)			52		
Total for 64-week treatment period (mL)					995.5
Total for study (mL)					1047.5

**Table 5 - Approximate sampled blood volume in ASMD patients in the child cohort (6 to <12 years) and in patients aged 3 to <6 years.**

Type	Volume per sample (mL)	Screening period		64-week treatment period	
		Number of samples	Total (mL)	Number of samples	Total (mL)
SMPD1 genotyping	3	1	3		
UGT1A1 genotyping	3	1	3		
CHIT1 genotyping	3	1	3		
ASM activity in leukocytes	3	1	3		
Serology tests: HIV, Hep C, Hep B	2.2	1	2.2		
Liver function	3	1	3	30	90
Clinical chemistry	4	1	4	11	44
Hematology	2	2	4	11	22
Coagulation	2.8	1	2.8	11	30.8
Safety biomarkers	6			30	180
Anti-olipudase alfa IgG and neutralizing antibodies in IgG positive patients	2.2			13	28.6
Efficacy biomarkers	3.8			4	15.2
Lipid profile	1.1	1	1.1	6	6.6
Serum bone-specific ALP and C-telopeptide	1			4	4
Sphingomyelin and metabolites in plasma and/or DBS	1.5			43	64.5
Olipudase alfa pharmacokinetics	1.5			24	36
Total for screening (mL)			29.1		
Total for 64-week treatment period (mL)					521.7
Total for study (mL)					550.8

See [Section 1.3](#) for additional information on sample collections based upon patient age.

**Table 6 - Approximate sampled blood volume in adolescent ASMD patients from birth to ≤2 years of age (infant/early child cohort).**

Type	Volume per sample (mL)	Screening period		64-week treatment period	
		Number of samples	Total (mL)	Number of samples	Total (mL)
SMPD1 genotyping	3	1	3		
UGT1A1 genotyping	3	1	3		
CHIT1 genotyping	3	1	3		
ASM activity in leukocytes	3	1	3		
CRIM testing	5	1	5.0		
Serology tests: HIV, Hep C, Hep B	2.2	1	2.2		
Liver function	1.1	1	1.1	29	31.9
Clinical chemistry	1.1	1	1.1	8	8.8
Hematology	1.2	2	2.4	10	12
Coagulation	1.4	1	1.4	11	15.4
Safety biomarkers	4.4			30	132
Anti-olipudase alfa IgG and neutralizing antibodies in IgG positive patients	1.1			13	14.3
Efficacy biomarkers	3.8			4	15.2
Lipid profile	1.1	1	1.1	6	6.6
Sphingomyelin and metabolites in plasma	1.5			29	43.5
Olipudase alfa pharmacokinetics	1.5			20	30
Total for screening (mL)			26.3		
Total for 64-week treatment period (mL)					309.7
Total for study (mL)					336

Additional blood samples may be required for circulating immune complex detection, IgE, serum tryptase, and complement activation following moderate, severe, or recurrent mild IARs suggestive of hypersensitivity reactions. Additional blood volumes are provided in [Table 7](#).

**Table 7 - Approximate sampled blood volume per infusion following moderate, severe, or recurrent infusion associated reactions suggestive of hypersensitivity reactions**

Type	Volume per sample (mL)
Circulating immune complex	3.5 mL
IgE antibodies	3.5 mL
Serum tryptase	3.5 mL
Complement	2 mL
Total per infusion	12.5 mL

## 10 STUDY PROCEDURES

### 10.1 VISIT SCHEDULE

[Section 1.2](#) summarizes the schedule of study events for all patients enrolled in the study, with specific requirements based upon patient age and gender. Details on the timing of study assessments are provided below and in [Section 1.3](#), [Section 1.4](#), [Section 1.5](#) and in [Section 10.3.2](#) through [Section 10.3.7](#). Individual evaluations are also described in [Section 9](#).

### 10.2 SCREENING AND INCLUSION PROCEDURES

During screening, the patient or a patient representative will receive information on the study objective(s) and procedures from the investigator. The patient and/or patient representative (parent or legal guardian) will have to sign the informed assent/consent prior to any action related to the study. Screening assessments as specified in [Section 1.2](#) may need several out-patient visits to the site or in-patient hospitalization may be required to proceed with all screening or baseline assessments. Two samples are to be collected greater than 24 hours apart during the screening period for platelet count assessments. The mean platelet count is to be used for determining patient eligibility.

Patients who meet all the inclusion criteria and none of the exclusion criteria will be eligible for inclusion into the study.

Retesting of any screening parameter is limited to a maximum of 3 times and with a minimum of 14 days in between reassessments. Unless indicated otherwise, the last retest value will be considered as the baseline value and reported in the e-CRF.

Screening procedures will be carried out within 60 days prior to the start of 64-week treatment period of DFI13803.

If a patient does not meet all inclusion criteria or meets one or more exclusion criterion within 60 days prior to the start of the treatment period, the patient may rescreen for the study once. For screening failures, the following data obtained during screening will be transferred to the e-CRF and entered into the database: patient's demographic data, inclusion and exclusion criteria, relevant medical history and surgical history (if available), previous and concomitant medications (if available), AE data (if available) and reason for failure.

## **10.3 TREATMENT PERIOD PROCEDURES**

Final inclusion in the study will be performed just before study drug infusion at Day 1/Week 0 of the treatment period.

Retesting of parameters during the treatment period is limited to one time, except for when the measurement has not been obtained in accurate conditions.

The dose escalation phase and the 64-week treatment period begins with the first intravenous infusion of 0.03 mg/kg olipudase alfa on Day 1/Week 0. The dose escalation phase ends with the first infusion at 3.0 mg/kg or with the identification of a patient-specific highest tolerated dose.

Day 1/Week 0 and Week 12 assessments and samples are to be collected per quarterly visit specifications, even though patients are actively dose escalating at these clinical visits. Samples are not to be collected in duplicate (ie, Week 12 quarterly visit and dose escalation visit) under such circumstances.

### **10.3.1 Hospitalization**

In-patient hospitalization will be required before and for at least 24 hours after infusion for all infusions during the dose escalation process through the second infusion at the highest tolerated dose. Patients may be required to stay in the hospital for additional time for safety purposes at the investigator's discretion. If discharged 24 hours after infusion, patients are required to return to the clinical site for assessments at 48 hours post infusion, and at 96 hours post infusion if necessary for pharmacokinetic samples.

After the second infusion at the highest tolerable dose, patients will be observed for a minimum of 3 hours following infusion completion, and may be discharged at the investigator's discretion. For quarterly visits at Week 26, Week 38 and Week 52 patients will be observed for a minimum of 3 hours following infusion completion, and may be discharged at the investigator's discretion. However, patients are required to return to the clinical site for assessments at 24 hours and 48 hours post infusion, and at 96 hours if necessary for pharmacokinetic samples.

